Delivery of interventions through telehealth and other types of technology (e.g., online, mobile apps) holds considerable promise for the field because of lower costs and greater reach, particularly for those living in rural areas. These considerations are particularly important in Vietnam and other LMIC because most older adults reside in rural areas. With the rapid adoption of mobile phones, tablets, and smartphones, family caregiver interventions hold considerable promise for closing gaps in dementia care and services for these countries. The COVID-19 pandemic has also reinforced the need for interventions that can be delivered at a distance to maintain support for caregivers and reduce their social isolation.

To our knowledge, our study will be the first study in Vietnam or other LMIC in Asia to examine the efficacy of multicomponent family caregiver intervention delivered remotely. The intervention has several components (e.g.,

PROTOCOL TITLE: A Phone Intervention for Family Dementia Caregivers in Vietnam

psychoeducation, stress reduction, skill-building) and is designed to reduce caregiver stress and burden.

4) Inclusion and Exclusion Criteria

Inclusion criteria:

To be eligible to participate, a family member will need to be the identified adult (i.e., age 18 and above) who is the primary informal (i.e., unpaid family member) caregiver (i.e., the person who provides the most time day-to-day care) to an older adult (i.e., age 60 and above) with dementia living in the community. If the primary caregiver is not available to participate, an alternate family member who provides substantial care (i.e., at least 4 h/day) to an older adult with dementia will be eligible to participate. In addition, caregivers will need to score ≥ 6 on the Zarit Burden Interview-4 (ZBI-4). All participants will be living in clusters in Thach That District, a semi-rural area in Hanoi.

Exclusion criteria:

The study will exclude:

- Caregivers with difficulties in the consent process due to cognitive impairment or severe sensory impairment (i.e., visual, hearing)
- Caregivers don't have access to phone
- Individuals who are not yet adults (i.e., infants, children, teenagers)
- Prisoners

5) Study Timelines

- We plan to begin recruitment in August of 2022.
- We plan to complete recruitment by January of 2023.
- We plan to complete all data collection and intervention activities by April of 2023.
- We plan to complete preliminary analyses of the data by July of 2023.

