Communes will be the unit of randomization and randomization assignments will be generated using a block randomization function in R for each stratum with a 1:1 ratio for two groups: intervention (n= approximately 8 clusters or 30 caregivers) or enhanced usual care (n= approximately 8 clusters or 30 caregivers). The UC Davis Biostatistician will be responsible for generating randomization codes and assigning randomization codes to communes. The biostatistician will communicate cluster assignment to the principal investigator (PI) to convey to the study team in Vietnam of when communes have been randomized.

Clusters will need to be in Thach That District and have a minimum of 3 participants and a maximum of 15 participants.

Blinding:

A trained outcome assessor who conducts data collection will be blinded regarding group assignments.

REACH VN Phone Intervention:

PROTOCOL TITLE: A Phone Intervention for Family Dementia Caregivers in Vietnam

Family caregivers in the intervention will receive a manualized multicomponent intervention, including psychoeducation, stress reduction, and skill-building, that will consist of 4-6 “core” sessions with the option for 1-2 “maintenance” sessions based on caregiver needs and clinical judgment with a trained staff (e.g., nurse, social worker, or community health worker) who has been certified to deliver the intervention. Interventionists will follow the interventionist manual that includes scripts, detailed descriptions of the goals for each session, and standardized forms.

The enrollment session (session 0) will be conducted face-to-face. Interventionists with village health workers will come to caregivers’ home to provide a caregiver notebook with information about dementia and management of common problems, check phone issues and signals, and conduct the risk priority intake assessment. The intervention sessions will be conducted over the phone with either audio or video call over the course of 1-3 months. The sessions will occur every 1–2 weeks depending on the needs and availability of family caregivers. Each intervention session will last between 30 minutes to an hour. In case caregivers are not able to concentrate on the session after the first 20-30 minutes, interventionists can end the session and make appointment to call back within 2-4 days (or whenever it is possible) to complete the session.

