### *Statistical Analysis Plan*

RCT outcomes include caregiver burden (primary) and depressive/anxiety symptoms (secondary). Preliminary analyses will compare the two groups at baseline on participant characteristics and primary outcomes using t-tests or chi-squared tests as appropriate; non-parametric versions will be used if needed. For each outcome, the primary assessment of efficacy will be based on intent-to-treat analyses. Difference scores on the outcomes between the two assessments will be computed. Within-group change will be assessed with a paired t-test or the Wilcoxon signed rank test, as appropriate, while between-group differences in change will be assessed with a two-sample t-test or the Wilcoxon rank sum test. If groups differ at baseline, analysis of covariance will be used with the 3-month assessment as the outcome and the baseline assessment as a covariate; group will be the primary predictor of interest and any additional participant characteristics found to be different at baseline will also be considered as covariates. Transformations or generalized linear models for non-normal data will be considered if model assumptions are violated. The data were imported into the REDcap database and analyzed using SAS statistical software. A p-value less than 0.05 is considered statistically significant.

Power analysis: With 30 participants per group, we will have 80% power to detect a difference as small as 0.64 standard deviations between the groups, assuming a one-sided test (as this is a pilot study) and alpha=0.05. If alpha is reduced to 0.025 to account for the two outcomes, the minimum detectable difference is 0.72 standard deviations. Our pilot RCT using the original REACH VN showed effect sizes of at least 0.9, so the current study is powered to detect smaller effects, which might be expected in a telehealth administration of the intervention.

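### The primary analysis moves from change scores to ANCOVA only on an undefined baseline difference; baseline-adjusted ANCOVA should be fixed in advance

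*SAP*

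**What the plan says.** The SAP (Statistical Analysis Plan section) first sets out baseline testing: "Preliminary analyses will compare the two groups at baseline on participant characteristics and primary outcomes using t-tests or chi-squared tests as appropriate". Its default efficacy test uses difference scores: "between-group differences in change will be assessed with a two-sample t-test or the Wilcoxon rank sum test". It then switches model on a condition: "If groups differ at baseline, analysis of covariance will be used with the 3-month assessment as the outcome". The baseline score becomes a covariate only in that case, and other covariates are also chosen from the data: "any additional participant characteristics found to be different at baseline will also be considered as covariates". The only significance level given is general and is not tied to the baseline tests: "A p-value less than 0.05 is considered statistically significant". The power paragraph works from a different basis, "assuming a one-sided test (as this is a pilot study) and alpha=0.05".

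The protocol does not settle the rule. Section 7 says that both groups are assessed at baseline and 3 months, that ZBI-6 is primary and PHQ-4 secondary, and that allocation is by commune: "Communes will be the unit of randomization and randomization assignments will be generated using a block randomization function in R for each stratum". The strata are not defined.

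**The concern.** The trigger could mean the outcome's own baseline score, any participant characteristic, or either, and no threshold is attached to it. Two analysts who both follow the SAP faithfully could therefore fit different primary models with different covariates. The baseline tests and the 0.05 level suggest a significance pre-test, but that is an inference from the text.

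Even on that reading the rule is a poor way to choose a model. A test of baseline balance with 30 per arm has little power, so moderate imbalances go unadjusted. Larger ones are adjusted, but only after they have been seen. Adjusting for the baseline score is worthwhile whether or not the arms look balanced, because it removes outcome variance. Preliminary efficacy is a stated objective with a named primary outcome, and with 60 caregivers precision is scarce.

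**Working it through.** **Inputs.** From the SAP: 30 per arm, 80% power, 0.64 SD at one-sided 0.05, 0.72 SD at 0.025. Assumed, because the documents do not give them: correlation ρ between baseline and 3-month scores of 0.3, 0.5 or 0.7; ratio k of baseline SD to 3-month SD; normal data; trigger at p<0.05 on the outcome's own baseline.

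**1. The plan's own figure.** Minimum detectable difference = (z_α + z_power)·√(2/30), with √(2/30) = 0.2582.
- α = 0.05 one-sided: (1.645 + 0.842) × 0.2582 = 0.642 SD.
- α = 0.025: (1.960 + 0.842) × 0.2582 = 0.723 SD.

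Both agree with the SAP. By the noncentral t, power at 0.64 is 79.0%. The SAP does not say whether the SD is of the raw score or of change.

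**2. What a p<0.05 trigger detects.** It fires at a gap of t(0.975, 58) × 0.2582 = 2.002 × 0.2582 = 0.52 SD. Its power is 21% for a true 0.3 SD difference and 48% for 0.5 SD. If any of m independent characteristics can trigger the switch, chance alone does so with probability 1 − 0.95^m: 5%, 23% and 40% for m = 1, 5 and 10.

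**3. Why unconditional ANCOVA is more precise.** In units of the 3-month variance, the change score has variance 1 + k² − 2ρk and the ANCOVA residual has 1 − ρ². The difference is (k − ρ)², which is never negative and is zero only when k = ρ. At equal SDs the ratio of ANCOVA to change-score variance is (1 + ρ)/2 = 0.65, 0.75 and 0.85.

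Normal approximation at ρ = 0.5, k = 1, effect 0.64 SD of the 3-month score:
- Change score, SD 1.000: 0.64/0.2582 − 1.645 = 0.834, power 79.8%.
- ANCOVA, SD 0.866: 0.64/(0.866 × 0.2582) − 1.645 = 1.217, power 88.8%.

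**4. Simulated power, SAP rule v ANCOVA always** (30 per arm, one-sided 0.05, effect 0.64 SD of the 3-month score, no clustering):

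| Baseline SD / 3-month SD | ρ = 0.3 | ρ = 0.5 | ρ = 0.7 |
|---|---|---|---|
| 0.7 | 77 v 82% | 87 v 88% | 96 v 96% |
| 0.85 | 73 v 82% | 84 v 88% | 96 v 96% |
| 1.0 | 68 v 82% | 80 v 88% | 94 v 96% |
| 1.3 | 57 v 82% | 69 v 88% | 85 v 96% |

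A ratio below 1 is plausible because entry requires a ZBI-4 score of at least 6, which may narrow the baseline spread. Nothing in the documents points to 1.3; that row only shows the range.

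**5. Other readings.**
- *0.64 in change-score SDs:* the change-score test has about 79%. The ANCOVA noncentrality is 2.479·√(2/(1 + ρ)), which gives about 91%, 88% and 84%.
- *Commune-level analysis* (8 communes per arm, assumed ICC 0.05, equal SDs): change in commune means v ANCOVA on commune means with 13 df is 58 v 71%, 71 v 78% and 88 v 90%.

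**6. Error rates, equal SDs, no clustering.** Under the null the rule has mean bias 0.00 and one-sided type I error of 4.3 to 4.7%, against 5.0% for ANCOVA.

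Conditional on a baseline gap g (in baseline SDs), the change-score estimate is shifted by (k − ρ)g in favour of the arm that started worse. In 10% of trials the intervention arm starts worse by an unflagged gap of 0.30 to 0.52 SD. The mean gap there is 0.2582 × (0.2031 − 0.0538)/0.100 = 0.39 SD. At ρ = 0.5 the shift is 0.5 × 0.386 = 0.19 SD, and the false-positive rate is 14%, against 5% for ANCOVA. In the mirror 10% the bias is 0.19 SD the other way and the false-positive rate 0.3%. With k = 0.7 the shift is 0.2 × 0.386 = 0.08 SD and the false-positive rate 9%.

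**7. Discretion.** If the loose wording let an analyst report whichever of the two tests was significant, one-sided type I error would be about 6.6 to 7.6%. This is something the text leaves open; it is not a claim about conduct.

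**The case against.** The strongest reply has four parts.

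*The trigger can be inferred.* Baseline tests and a 0.05 level appear in the same paragraph. That is a fair reading, but it does not say which variables count, and covariates are still only to be considered.

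*There is no average harm.* This stands: applied mechanically, the rule is unbiased over randomisations and slightly conservative. The 14% false-positive rate belongs to a selected tenth of trials and is offset by 0.3% in the mirror tenth.

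*The power loss rests on assumptions.* This also stands. At SD ratio 0.85 the loss is about 4 points at ρ = 0.5 and nil at 0.7. On the change-score-SD reading the default test essentially meets its planned power. A wider trigger invokes ANCOVA more often: with ten independent tests and equal SDs the rule reaches 73, 83 and 95%, against 81, 88 and 96% for ANCOVA. The loss shrinks in these cases, but in none does the rule beat unconditional ANCOVA by more than simulation noise.

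*A commune-level model costs far more than one degree of freedom.* True, but that cost comes from randomising communes and applies equally to change scores. With the baseline covariate charged (13 df), ANCOVA still has the higher power.

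That this is a pilot limits how much weight the efficacy test carries. It is no reason to leave the primary model open.

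**Conclusion.** The concern holds. The SAP does not fix its primary model or its covariates, and no other part of the documents does so. Against unconditional ANCOVA the rule loses about 14, 8 and 2 points of power at ρ = 0.3, 0.5 and 0.7 with equal SDs. The loss is smaller if the baseline SD is the lower of the two, and about nil when the SD ratio equals ρ. On the raw-score reading of 0.64 SD with equal SDs, the rule reaches the planned 80% at ρ = 0.5 but not at 0.3. These figures depend on the assumed ρ, SD ratio and trigger. They ignore dropout and, except for the commune-level check, clustering, so absolute powers are optimistic and the comparison is what matters. There is no average bias and no type I inflation if the rule is applied mechanically; the bias is conditional on the imbalance observed. This is a change the sponsor should make, though it is not a fatal flaw.

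**What to change.** Make ANCOVA the single primary analysis for ZBI-6 and PHQ-4 whatever the baseline comparison shows: 3-month score on arm and baseline score, in a model that accounts for commune. Delete the baseline-difference trigger and the rule that adds characteristics found to differ. Name any further covariates in advance; the randomisation stratum can be one of them only once the protocol defines it. Keep baseline comparisons descriptive. The change-score test can stay as a labelled sensitivity analysis.

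The cost is SAP wording and about one degree of freedom for the baseline covariate. The degrees of freedom given up to commune follow from the cluster design, not from this change. No new data are needed, since both scores are already planned in both arms.

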Study Title: A pilot cluster randomized controlled trial of a phone intervention supporting family caregivers of people living with dementia in Vietnam: Resources for Enhancing Alzheimer's Caregiver Health in Vietnam (REACH VN)

NCT#: NCT05481320

Document Date: November 16, 2022

Document Type: Study Protocol

1) Protocol Title

Title: A Phone Intervention for Family Dementia Caregivers in Vietnam

Protocol Version Date: *11/16/2022*

2) Objectives

The objective of this study is to examine the feasibility, acceptability, and preliminary efficacy of the phone version of REACH VN, a psychosocial culturally adapted Alzheimer's family caregiving intervention that will be delivered over the phone with an enhanced control as the comparison. The pilot cluster RCT will test the hypothesis that family caregivers who receive the intervention will show lower caregiver burden (primary outcome) and lower depressive/anxiety symptoms (secondary outcome) compared with those in the control group.

3) Background

Low- and middle-income countries (LMIC) such as Vietnam are undergoing a dramatic demographic transition that will result in a substantial increase in the number of older adults, including those afflicted with Alzheimer's disease and related dementias (ADRD), over the next several decades. Dementia is among the most disabling and costly neurodegenerative brain diseases. Strengthening LMIC capacity to support family caregivers of people with dementia through low-cost and sustainable non-pharmacological approaches, such as education and skill-building to deal with difficult behaviors, is vital to avoid costly and ineffective alternatives such as psychotropic medications or institutionalization, and to reduce caregiver burdens and depression. While evidence-based non-pharmacological treatments exist in high income countries (HIC), these interventions have not been adapted for use in Vietnam and other LMIC.

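### Does the SAP's p<0.05 rule need to state its sidedness, and whether the 0.025 for two outcomes applies?

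*SAP*

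**What the plan says.** The SAP's Statistical Analysis Plan paragraph describes three kinds of test before giving its threshold.

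- Baseline: it will "compare the two groups at baseline on participant characteristics and primary outcomes using t-tests or chi-squared tests as appropriate".
- Within group: paired tests of change.
- Efficacy: "between-group differences in change will be assessed with a two-sample t-test or the Wilcoxon rank sum test".

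It also provides for a covariate-adjusted model: "If groups differ at baseline, analysis of covariance will be used with the 3-month assessment as the outcome". The paragraph ends with "A p-value less than 0.05 is considered statistically significant", with no side, test or outcome named.

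The Power analysis paragraph comes next. Its calculation is made "assuming a one-sided test (as this is a pilot study) and alpha=0.05". It then adds: "If alpha is reduced to 0.025 to account for the two outcomes, the minimum detectable difference is 0.72 standard deviations". It compares these figures with effect sizes of at least 0.9 from the earlier face-to-face pilot, "so the current study is powered to detect smaller effects, which might be expected in a telehealth administration of the intervention".

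Protocol section 2 (Objectives) states the hypothesis with a direction: "lower caregiver burden (primary outcome) and lower depressive/anxiety symptoms (secondary outcome) compared with those in the control group". Protocol section 7 (Outcome assessments) repeats the ranking, with ZBI-6 primary and PHQ-4 secondary. The Protocol gives no alpha, sidedness or multiplicity rule.

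**The concern.** A power assumption is not formally a decision rule. Read alone, the threshold could be one-sided or two-sided, and the choice moves the critical value. It also cannot carry one meaning throughout its paragraph: a baseline comparison looks for a difference in either direction, while the hypothesis about burden and symptoms points one way. The conditional 0.025 raises a second question, namely whether each outcome is tested at 0.05 or at half that. The baseline sentence adds some doubt by putting the primary outcome in the plural.

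At stake is how a modest ZBI-6 or PHQ-4 result is labelled. The SAP allows that telephone delivery may give effects below 0.9 SD, and sidedness matters more there than at 0.9 SD. An unstated side could also, in principle, be chosen after the results are seen.

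**Working it through.** **Inputs.** From the SAP power paragraph: 30 per group, 80% power, alpha 0.05 one-sided, alternative alpha 0.025, printed detectable differences 0.64 and 0.72 SD, earlier effect size 0.9. Like the SAP's own calculation, this makes no allowance for communes or dropout.

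**1. The printed figures.** Detectable difference = (z for alpha + z for power) × √(2/n), with √(2/30) = 0.2582.

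- One-sided 0.05: (1.645 + 0.842) × 0.2582 = 0.642 SD (0.650 by noncentral t). Printed: 0.64.
- One-sided 0.025: (1.960 + 0.842) × 0.2582 = 0.723 SD (0.736 by noncentral t). Printed: 0.72.

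Both reproduce, and both on a one-sided basis. A two-sided 0.05 test has the same critical value as one-sided 0.025, so it would pair with 0.72 SD and not with the headline 0.64 SD. Two-sided 0.025 would give 0.796 SD, which is printed nowhere. The figures therefore show that the authors worked one-sided throughout.

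**2. Cost of the other reading.** Power = Φ(d/0.2582 − z for alpha). At d = 0.64, d/0.2582 = 2.479, so power is Φ(2.479 − 1.645) = 79.8% one-sided and Φ(2.479 − 1.960) = 69.8% two-sided.

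| True difference | One-sided 0.05 | Two-sided 0.05 | Readings disagree |
|---|---|---|---|
| 0.64 SD | 80% | 70% | 10% |
| 0.72 SD | 87% | 80% | 8% |
| 0.9 SD | 97% | 94% | 3% |

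By noncentral t the first row is 79% and 68%, a gap of 10.6 points.

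With no true effect, the readings disagree on a claim of benefit when the statistic lies between the two critical values: 5% − 2.5% = 2.5%. The two-sided test also rejects in the harmful tail, another 2.5%, so total disagreement is 5%.

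**3. Where a label would change.** For the unadjusted t-test with 58 df, the critical observed differences are 1.672 × 0.2582 = 0.43 SD one-sided and 2.002 × 0.2582 = 0.52 SD two-sided. Only an observed benefit between these is labelled differently. If communes were allowed for (8 per arm of 3.75 caregivers, 14 df, design effect 1 + 2.75 × ICC, ICC assumed at 0.01 or 0.05), the band becomes 0.46–0.56 or 0.49–0.59 SD.

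**4. Two outcomes.** If both outcomes were confirmatory, independent and tested at 0.05, with either one counting as success, the chance of at least one false positive would be 1 − 0.95² = 9.75%. At 0.025 each it is 1 − 0.975² = 4.9%. The documents do not set up that situation: they name one primary and one secondary outcome and state no rule under which either alone makes the trial a success.

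**5. Baseline tests.** The one-sided statement concerns the power to detect a difference between groups on the outcomes. Nothing extends it to baseline characteristics, and a chi-squared comparison of those has no natural one-sided form. Nor does the SAP tie its condition for using analysis of covariance to p<0.05; it says only that the groups differ.

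**The case for a change.** The strongest case for a change is that the threshold and the sidedness sit in different paragraphs with different jobs, so the analyst must infer the rule. The term t-test has to mean two-sided at baseline and one-sided for efficacy within one paragraph. The SAP itself raises an alpha split and leaves it unresolved, assesses efficacy outcome by outcome, and uses a plural for primary outcomes. Preliminary efficacy is a stated objective, and about 10 points of power separate the readings at 0.64 SD. Fixing the side in writing would cost a sentence or two and would rule out a later choice.

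Most of the factual part stands: the side is not repeated beside the rule, and the 0.025 is only conditional. The inference is not a hard one, however. The same 0.05 appears in the next paragraph with its side and a reason, the hypothesis has a direction, and no text says two-sided. The 0.025 reads naturally as an extra sensitivity figure for readers who want both outcomes covered. The plural looks like a slip beside the explicit ranking in the SAP's opening sentence and in Protocol sections 2 and 7.

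**Conclusion.** No change is needed. Following the plan on its natural reading (a one-sided 0.05 test on ZBI-6, PHQ-4 secondary, ordinary two-sided baseline and within-group tests) gives no wrong result, and both printed detectable differences are correct on that basis. The gap is one of wording, and an analyst fills it from the adjacent text.

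The consequence of misreading is bounded. Two-sided testing would take power at 0.64 SD from about 80% to about 70% and would alter the label only for observed benefits of roughly 0.43 to 0.52 SD in the unadjusted comparison. For a symmetric test such as the t-test, a reader given the p-value and its direction can convert one reading to the other. The documents describe a feasibility, acceptability and preliminary-efficacy pilot and tie no later decision to crossing 0.05.

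This rests on 30 per arm with independent observations, as the SAP assumes; the ICCs used for the shifted band are assumptions, since the documents give none. Whether clustering by commune should enter the analysis is a separate question. The conclusion covers the SAP text available for review.

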A research assistant at the National Geriatric Hospital who is trained and certified will conduct outcome assessments over the phone. An outcome assessor will be masked to group assignment status. We will remind caregivers not to tell an outcome assessor their group assignment status to minimize bias. Caregivers in both groups will be assessed at baseline and 3 months. The primary outcome will be caregiver burden as assessed by the Zarit 6-item burden scale (ZBI-6) and the secondary outcome will be depressive/anxiety symptoms as assessed by the four-item Patient Health Questionnaire (PHQ-4). We will use previously developed Vietnamese versions of study instruments.

Feasibility, fidelity, and acceptability assessments:

Feasibility metrics will include recruitment, randomization, retention, treatment adherence, treatment fidelity, and assessment processes. *Fidelity assessment* will be based on review of standardized treatment delivery forms completed by interventionists and an independent observer of a random subset of sessions. Prior to the RCT, interventionists who are already certified in face-to-face REACH VN intervention will need to be trained in phone delivery. *Acceptability* will be assessed through semi-structured interviews with a random subset of participants who have completed the intervention group (n=10) and REACH VN interventionists (n=5). These interviews will include questions on satisfaction, aspects of the intervention that participants found most helpful, challenges, and opportunities for improvement. We will inquire about any issues related to intervention delivery by audio or video call.

Reimbursement:

Participants will receive \$4 (or 100,000 VND) at the end of the screening session and \$8 (or 200,000 VND) at the end of each study visit/session (including intervention sessions and outcome assessments).

8) Data and/or Specimen Management and Confidentiality

REDCap will be used to collect outcomes data. Procedures for maintenance and confidentiality include 1) assigning each participant a unique identifier, 2) data collected will be labeled using the unique identifier and will be stored separately

PROTOCOL TITLE: A Phone Intervention for Family Dementia Caregivers in Vietnam

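### Communes are randomised, but the between-group tests have no commune term and the stated 80% power assumes 60 independent, fully retained caregivers

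*SAP*

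**What the plan says.** Protocol section 7, under Randomization, sets the design: "Communes will be the unit of randomization and randomization assignments will be generated using a block randomization function in R for each stratum". The planned size is "intervention (n= approximately 8 clusters or 30 caregivers", with the same numbers in the control arm, and each commune must "have a minimum of 3 participants and a maximum of 15 participants".

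The SAP's analysis paragraph works on individual caregivers. "Difference scores on the outcomes between the two assessments will be computed", and then "between-group differences in change will be assessed with a two-sample t-test or the Wilcoxon rank sum test". If the groups differ at baseline, "analysis of covariance will be used with the 3-month assessment as the outcome and the baseline assessment as a covariate". The only further covariates it names are participant characteristics that are out of balance at baseline, and generalized linear models are reserved for non-normal data. Significance is set at p below 0.05, with no statement of sidedness.

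The SAP's power paragraph says "With 30 participants per group, we will have 80% power to detect a difference as small as 0.64 standard deviations", one-sided at 0.05, and gives 0.72 SD if alpha is 0.025 for the two outcomes. It adds that the earlier pilot showed effects of at least 0.9, so that this study can detect smaller ones. It mentions no ICC, design effect, number of communes or loss to follow-up. Retention appears in the protocol only as something to be measured: "Feasibility metrics will include recruitment, randomization, retention, treatment adherence, treatment fidelity, and assessment processes".

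**The concern.** Caregivers in one commune share an allocation and may share influences on the outcome. If their outcomes are correlated, a test that treats them as independent uses too small a standard error and rejects a true null too often. This is the weightier half of the point, because a positive result would look stronger than it is.

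The power paragraph makes the same assumption of independence, and it also assumes that every caregiver is followed up. A commune-adjusted test would not have the stated power, so readers of a null result would overrate what the trial could have detected.

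**Working it through.** **Inputs from the documents:** 30 caregivers and about 8 communes per arm (protocol section 7); one-sided alpha of 0.05 or 0.025 and 80% power (SAP). **Assumptions, because the documents give no figure:** ICC of the analysed outcome 0.01 / 0.05 / 0.10 / 0.20; loss of 0% or 15%.

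**1. The SAP's own figures.** Minimum detectable difference (MDD) for independent caregivers = (z for alpha + z for power) × √(2/30):
- 0.05: (1.645 + 0.842) × 0.2582 = 0.642
- 0.025: (1.960 + 0.842) × 0.2582 = 0.723

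Both match the SAP, with no allowance for clustering or loss.

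**2. Design effect.** Mean commune size is 30/8 = 3.75, so DE = 1 + 2.75 × ICC = 1.0275 / 1.1375 / 1.275 / 1.55.

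**3. Type I error of the unadjusted test.** At nominal one-sided 0.05 it is approximately 1 − Φ(1.645/√DE) = 5.2 / 6.2 / 7.3 / 9.3%. Simulated t-tests with six communes of 4 and two of 3 per arm agree within about 0.2 point. Rounded working figures are 5.3 / 6.2 / 7.3 / 9.5%. Run two-sided, the t-test rejects about 6.7 / 8.4 / 11.8% at ICC 0.05 / 0.10 / 0.20.

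**4. Commune-adjusted test.** SE = √((2/30) × DE), noncentral t with 16 − 2 = 14 df. For 80% power the noncentrality must be 2.616 (alpha 0.05) or 3.013 (alpha 0.025), so MDD = 2.616 × SE or 3.013 × SE. Equal communes, complete data:

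| ICC | SE | Power at 0.64 SD (0.05) | MDD (0.05) | Power at 0.72 SD (0.025) | MDD (0.025) |
|---|---|---|---|---|---|
| 0 | 0.258 | 76% | 0.68 | 74% | 0.78 |
| 0.01 | 0.262 | 75% | 0.68 | 73% | 0.79 |
| 0.05 | 0.275 | 71% | 0.72 | 68% | 0.83 |
| 0.10 | 0.292 | 67% | 0.76 | 63% | 0.88 |
| 0.20 | 0.322 | 60% | 0.84 | 55% | 0.97 |

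The ICC 0 row isolates the degrees of freedom: about 4 points are lost at 0.64 SD and 6 at 0.72 SD before any correlation enters.

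**5. Loss to follow-up.** With an assumed 15% loss there are 25.5 per arm, mean commune size is 3.19 and DE = 1 + 2.1875 × ICC. The MDD becomes 0.74 / 0.77 / 0.81 / 0.88 SD (0.05) and 0.85 / 0.89 / 0.93 / 1.01 SD (0.025).

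**6. The 0.9 sentence.** At 0.025, set 3.013 × SE = 0.9 and solve for the ICC:
- Complete data: DE = 0.81 × 15 / 3.013² = 1.338, so ICC = 0.338/2.75 ≈ 0.12.
- 15% loss: DE = 0.81 × 12.75 / 3.013² = 1.138, so ICC = 0.138/2.1875 ≈ 0.06.

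At one-sided 0.05 every MDD in steps 4 and 5 is below 0.9.

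**7. Unequal communes.** With 8 communes, 30 caregivers and at least 3 in each, the largest possible commune has 30 − 7 × 3 = 9. For seven of 3 and one of 9, the commune variance is v = ICC + (1 − ICC)/m. With known variance components the random-intercept SE is √(2/Σ(1/v)). With 14 df the MDD is 0.69 / 0.73 / 0.78 / 0.86 SD (0.05) and 0.79 / 0.84 / 0.90 / 0.99 SD (0.025).

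**The case against.** **Pilot status.** The trial's stated aims are feasibility, acceptability and preliminary efficacy. That limits the severity. But the protocol's Objectives section also states an efficacy hypothesis, and the SAP sets a significance threshold and claims 80% power, so the test and the claim should fit the design.

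**The ICC may be small.** This stands. Stable differences between communes cancel in a change score, and at ICC 0.01 the type I error is only about 5.3%. The argument does not carry over directly to the ANCOVA, which models the 3-month score.

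**14 df is the reviewer's choice.** This also stands. A random intercept with data-driven df could have more than 14 when commune variance is near zero, so the adjusted power figures are conservative.

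**The planned test keeps most of its power.** At ICC 0.10 the unadjusted t-test still rejects about 76% of the time at 0.64 SD. It does so with a real one-sided error of about 7.3%, so the figure is not comparable with 80% power at 5%.

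**Stronger readings that do not hold.** A reader might infer that the power calculation is wrong as arithmetic; it is not, since both figures reproduce for independent caregivers. A reader might also infer, from the upper limit of 15 per commune, that very uneven communes could remove the margin below 0.9 SD at both alpha levels. With the planned 8 communes and 30 caregivers per arm, a commune of 15 is impossible. The most uneven split gives at most 0.86 SD at one-sided 0.05 up to ICC 0.20. Removing the margin at that level would take materially fewer communes than planned, or a higher ICC or heavier loss than shown.

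**Conclusion.** The point holds as a mismatch between design and analysis. The between-group tests ignore the unit of randomisation, and the stated power belongs to an individually randomised trial with full retention.

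The type I error of the planned test exceeds nominal whenever the ICC is positive: slightly at 0.01, and to nearly double at 0.20. The power shortfall of an adjusted test is moderate at low ICC because communes are small, and part of it reflects the 14 df. The claim about effects below 0.9 SD is weakened and not overturned: it is secure at one-sided 0.05 in the scenarios shown, and conditional on ICC and loss at 0.025.

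The sizes rest on assumed ICCs and an assumed loss rate. Part of the SAP file was not available for this review, so the finding rests on the Statistical Analysis Plan section, which contains both the tests and the power paragraph. It should be fixed.

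**What to change.** 1. **Analysis.** Make the between-group comparison, whether on change or by ANCOVA, account for commune. Use a random intercept for commune with small-sample degrees of freedom, or a t-test on commune means. Apply any rank test to commune means.
2. **Power paragraph.** State that about 8 communes and 30 caregivers per arm are randomised. Give the MDD at 80% power (14 df, equal communes, complete data) for assumed ICC 0.01 / 0.05 / 0.10 / 0.20 as about 0.68 / 0.72 / 0.76 / 0.84 SD at one-sided 0.05 and 0.79 / 0.83 / 0.88 / 0.97 SD at one-sided 0.025. Add that loss to follow-up, unequal communes or fewer communes make these larger; with an assumed 15% loss at ICC 0.10 they are about 0.81 and 0.93 SD. Say whether the SD is that of the change score or of the 3-month score.
3. **The 0.9 sentence.** Say that with about 8 communes per arm it holds with a smaller margin at one-sided 0.05 in these scenarios. At one-sided 0.025 it holds only up to an ICC of about 0.12 with complete data, or about 0.06 with an assumed 15% loss.

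**Cost.** Enrolment and procedures do not change. The stated detectable differences become less favourable, and the adjusted test has lower nominal power than the unadjusted one: about 67% against 76% at 0.64 SD with ICC 0.10, one-sided 0.05.
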